Patient eligibility for PGx testing will be determined by the pharmacist and will be done within the context of standard practice at that pharmacy. For patients that express interest in testing, the pharmacist will send a notification letter about the test and the test requisition form to the prescribing provider of the eligible medication for his/her signature. If the provider returns the signed form, pharmacists will invite the patient to the pharmacy to discuss testing. Pharmacists will be encouraged to disseminate the test information sheet to patients when testing is initially discussed (see component #1 of the toolkit); the research study team will provide copies of the handout to each participating pharmacy. The test lab will send the pharmacist an interpretative summary report (genotype and phenotype) and the pharmacist will send a copy of the report to the prescriber on record. The interpretation of test results and communication of results with patients and their prescribing provider are at the sole discretion of the pharmacist. The study pharmacist will be available to the community pharmacists to assist with questions regarding testing processes/procedures, interpretation of results, or treatment recommendations. All pharmacist interactions will be noted for data analysis, including the nature of the interaction and time spent per interaction.

MTM + PGx Testing Arm. A licensed pharmacist will be required to conduct each MTM session in the MTM + PGx study arm. There will be two MTM sessions: MTM #1 will be conducted in-person and MTM #2 will be conducted in-person or by phone. The five core elements of a standard MTM will be included.³²

- **MTM Session #1:** The MTM session will include review of the patient's medications, the medical history, most recent lab values if available/known, and medication history. Patients will be encouraged to bring a list and, if possible, the actual containers of both prescription and over-the-counter medicines. The information will be recorded in a standardized MTM form (Appendix 3). The pharmacist will document barriers and possible recommendations to increase adherence in the MAP (Appendix 4). At the completion of the session, the pharmacist will review PGx testing, including the purpose of testing, description of test, test limitations, and anticipated outcomes. Pending patient consent for testing as required by the lab, a buccal sample will be collected and sent for testing.

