PGx Testing Only Arm. Participants in this arm will receive only PGx testing. Prior to testing, the pharmacist will review PGx testing with the patient, including the purpose of testing, description of test, test limitations, and anticipated outcomes, using any of the toolkit resources provided as desired/needed. Upon patient consent, a buccal sample will be collected and sent for PGx testing. When testing is completed, the pharmacist will review the PGx results and the participant's medication history to determine if drug or dosage adjustments should be considered based on the test results. Results may be provided to the patient using the PGx wallet card or patient test report provided in the toolkit. If the patient is taking another medication impacted by the same PGx gene and there is strong evidence regarding dose adjustment/drug selection based on genotype, recommendations for additional drug or dosing changes will be made. The pharmacist will contact all patients to discuss their result, even for patients with a "normal" test report, and if any changes to their medications are indicated. The pharmacist will also contact the participant's provider if changes are indicated. In the event that MTM is clinically indicated for a patient who undergoes PGx testing in this arm, pharmacists should provide the service and we will exclude these patients from the study.

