and can read and write in English, and have a new or existing prescription (<1 year active) for a drug listed in Table 1 to be eligible to participate. Each pharmacy will identify existing patients eligible for testing through a query of their database for active prescriptions for the selected drugs. If more than 30 patients in a pharmacy are identified by the database search, we will ask pharmacists to contact patients with the newest prescriptions. Patients will be contacted by phone or in-person by the pharmacist to introduce the study. Interested patients will be asked to visit the pharmacy to learn more about testing, sign the consent form requested by the testing laboratory, and provide a DNA sample (buccal swab). Patients who have had PGx testing for one of the genes in Table 1 or had an MTM within the past 12 months will be ineligible. All women and minorities who meet the study inclusion criteria will be eligible to participate in the study. Based on our power calculations, we estimate that we would need to enroll 18 patients per cluster (360 total).

Patients who consent to testing based on their pharmacist's recommendation will be asked to provide a buccal swab for DNA extraction. Patient samples will be sent for testing to Pathway Genomics laboratory. Testing will be provided at no cost for participants. As the Pathway Genomics' clinical tests are currently available to any clinician, only the consent required by the testing lab will be required of the patient.

Patients in the control arms will be identified by each participating pharmacy; two controls will be identified per each participant in the PGx arms (2:1) and matched on drug, age and gender. Time on treatment, medication changes (dose/drug selection), and refill history (adherence) data will be collected along with demographic data and compared to patients in the PGx testing arms. Based on their pharmacy records, patients who have undergone MTM or PGx testing outside of the study will be excluded from the control arm.

Risk/Benefit Assessment. If patients decide to have pharmacogenetic testing, a buccal swab sample is required. There are no known risks to a buccal swab sample. The sample, or DNA extracted from the sample, will be sent to the laboratory and stored only for the time necessary laboratory regulations.

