The integration of PGx testing into the community pharmacy setting will be assessed primarily through surveys of patients and pharmacists. In addition, we will conduct semi-structured interviews with a subset of pharmacists to gather more in-depth understanding of their experiences, perceived barriers, and likelihood to continue to offer PGx testing. The measures to be assessed are described below; clinical outcome measures will be collected about the medications impacted by PGx only.

Patient Surveys (Aim 2b) The baseline survey will collect demographic data, prior knowledge about PGx, self-reported co-medications, time on treatment for PGx-related drug(s), and medication adherence (see Table 2; Appendix 5). The follow-up survey will gather data on 1) satisfaction with the testing experience in a pharmacy setting, including use/provision of patient materials from Aim 1; 2) perceived value of testing; and 3) comprehension of test result. Additional measures include medication-taking behaviors and information-sharing. The follow-up survey will be administered approximately one month after the PGx results are communicated since many of the medications are prescribed in 90-day allotments. Key survey questions are further described below; data on age, gender, co-medications, and time on treatment for PGx-related drug(s) will also be collected for controls.

- [Baseline] Literacy. We will screen for health literacy using the validated single question: “How confident are you filling out forms by yourself?” Compared to the gold standard literacy tools REALM or S-TOFHLA, this single question accurately predicts inadequate health literacy⁹⁹ and is more feasible to administer.
- [Follow-up] Comprehension of Results. Our primary outcome will be comprehension of test results based on gist recall of the phenotype.¹⁰⁰ Specifically, the outcome of interest is the patient’s recognition of the presence or absence of a variant gene. Due to the complexity of genotypes and presumed patient unfamiliarity with gene nomenclature, we do not believe it reasonable to expect patients to recall their genotype. Therefore, we will instead ask patients to circle their specific metabolizer status (e.g., rapid, extensive, intermediate, poor, or inconclusive). For the genes *SLCO1B1* and *VKORC1*, we will ask patients to indicate their test

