Patient Study Population. Patients will be invited to complete two surveys: 1) a baseline survey after they consent to testing and 2) a follow-up survey after they receive the test results. A brochure will be provided to the patient that will describe the purpose of the survey, risks and benefits, participant rights, investigator contact information, and how to access the survey. The pharmacist can ask if the patient would be willing to be contacted by the study coordinator or to complete the survey on their own time online. Upon completion of the baseline survey, participants will be asked to indicate if they would be interested in participating in the follow-up survey and re-contacted.

Pharmacist Study Population. Participating pharmacists will be invited to complete the baseline survey prior to the start of the in-person training session. The instructor (the clinical pharmacist on the research team) will describe the purpose of the survey, risks and benefits, participant rights, investigator contact information, and how to access the survey online (paper copy will also be available upon request). For the post-study interviews, pharmacists will be contacted at the completion of the study to ascertain interest to be interviewed.

Survey Administration. We will use Redcap, an online survey tool to design and administer the surveys. Redcap offers features that allow for custom designs, branching/skip logic, randomization of answer choices, multiple collection features and data output formats. A customized link will be sent to each participant to access the survey set, enabling the study coordinator to track and link responses between survey sets and to send reminders to only those who do not respond. Paper or phone option will be made available as requested; pharmacies can elect which method they prefer at the start of the study.

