Sensitivity analyses will be performed to examine the impact of reported changes in comprehension, as individuals who drop out could potentially be less likely to change behaviors. The results of complete case and imputed analyses will be reported. The type of missing data will be examined to understand whether they are missing at random (MAR) or not. If they are, then the assumption will be that the imputed analyses provide the better estimate of the treatment differences. If the decision is that one cannot say that the data were MAR, then both results will be presented with accompanying text describing the potential biases in both sets of results, the level and type of missingness seen, as well as the limitations of interpretations if a significant number of observations were missing.

STUDY SAFETY MEASURES

Safety Measures

This study does not contain any safety endpoint measures.

Pregnancy Guidelines

Pregnant females are eligible to participate in this study if they meet the inclusion criteria. There is no known risk to the mother or unborn child as a result of this study.

Safety Monitoring

Federal regulations require prompt reporting to the IRB, appropriate institutional officials, sponsor, coordinating center and the appropriate regulatory agency head of unanticipated problems involving risks to subjects or others that occur in the course of a subject's participation in a research study at DUHS. (45 CFR 46.103(b)(5)(i) and 21 CFR 56.108(b)(1)).

Investigators are responsible for monitoring the safety of patients who have entered this study and for alerting the study team to any event that seems unusual, even if this event may be considered an unanticipated benefit to the patient.

The Principal Investigator will continuously monitor and tabulate adverse events. Appropriate reporting to the Duke University Medical Center IRB will be made. The Principal Investigator or designee will also continuously monitor the conduct, data, and safety of this study to ensure that:

- Interim analyses occur as scheduled;
- Risk/benefit ratio is not altered to the detriment of the subjects;
- Appropriate internal monitoring of adverse events and outcomes is done;
- Over-accrual does not occur;
- Under-accrual is addressed with appropriate amendments or actions;
- Data are being appropriately collected in a reasonably timely manner.

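### The PGx-only arm removes tested patients who turn out to need MTM, while the MTM arm keeps them, which can bias the primary and other follow-up comparisons

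*Combined protocol and SAP*

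**What the plan says.** The rule closes the paragraph on the PGx Testing Only Arm in Part II. Its trigger is "In the event that MTM is clinically indicated for a patient who undergoes PGx testing in this arm"; its consequence is that "pharmacists should provide the service and we will exclude these patients from the study". No criterion for the indication is given, and no time point.

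The paragraph on the MTM + PGx Testing Arm has no counterpart. MTM is part of the intervention there: "There will be two MTM sessions: MTM #1 will be conducted in-person and MTM #2 will be conducted in-person or by phone".

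Three other places bear on the point:

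- **Patient Study Population (Part II):** in both arms, patients who "had an MTM within the past 12 months will be ineligible".
- **Patient Surveys and survey population (Part III):** "Our primary outcome will be comprehension of test results based on gist recall of the phenotype". "Patients will be invited to complete two surveys", one after consent to testing and one after the result. The second comes about a month after the result is communicated, and refill data run for six months.
- **Data Analysis:** a logistic mixed model with treatment as fixed and cluster as random effect. No analysis population or as-allocated rule is stated. The sensitivity analyses are motivated by the worry that "individuals who drop out could potentially be less likely to change behaviors".

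**The concern.** Pharmacies are allocated first and patients are tested afterwards, so this exclusion follows allocation. It applies to one arm only. In practice it rests on a pharmacist who knows the arm, and nothing in the text prevents it from being applied once the test result is known.

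A difference between the arms could then reflect who was removed rather than what MTM does. The plan itself makes a link between need and outcome plausible: under Aim 2a it expects older, chronically ill and less educated patients to gain more from MTM in comprehension and satisfaction. Such patients may well be those judged to need it.

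Comprehension, satisfaction and adherence are exposed. Acceptance counted at consent and the pharmacist-level outcomes are not directly affected. Because excluded patients leave the study, their follow-up data may never exist, and the analysis could not repair the loss later.

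**Working it through.** **Does anything in the plan offset the rule?**

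- The 12-month bar screens for past receipt of MTM, equally in both arms. It does not screen for current need.
- The mixed model accounts for clustering, not for who was removed.
- The missing-data text deals with drop-out, not with patients the study itself takes out.

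**Inputs from the documents.** 20 pharmacies × 18 patients = 360, which matches the stated total. I take 10 pharmacies and 180 patients per arm. The documents give no comprehension rate, ICC, share of patients with an MTM indication or outcome difference for them, so the values below are assumptions.

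**Notation.**

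- *q*: share of patients for whom MTM is indicated, the same in both arms.
- *d0*: how far their comprehension would fall below that of other patients without MTM.
- *t*: what MTM adds in these patients.
- *d = d0 − t*: their remaining deficit after the MTM they are given.

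**Bias.** Let P be the proportion correct among non-indicated PGx-only patients. Analysed as allocated, that arm averages (1 − q)P + q(P − d) = P − qd. With the exclusion it averages P. The MTM-minus-PGx difference therefore shifts by **−q × d**.

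**Numbers with no true MTM effect (t = 0, so d = d0), 70% correct overall.** For q = 20% and d = 20 points:

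- Non-indicated: 0.70 + 0.2 × 0.2 = 0.74. Indicated: 0.74 − 0.20 = 0.54.
- MTM arm: 0.8 × 0.74 + 0.2 × 0.54 = 0.70. PGx-only arm after exclusion: 0.74, with 180 × 0.8 = 144 patients left.
- Spurious difference: 0.70 − 0.74 = −4 points.
- At ICC 0, SE = √(0.70 × 0.30/180 + 0.74 × 0.26/144) = 0.050, so the shift is 0.80 SE and a two-sided 5% test rejects with probability 0.126.
- At ICC 0.05, the design effects are 1 + 17 × 0.05 = 1.85 and 1 + 13.4 × 0.05 = 1.67, SE = 0.066, and the probability is 0.093.

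**Simulation.** 20,000 trials per setting, with normal pharmacy shifts of variance ICC × 0.7 × 0.3. The test is a t-test on the pharmacy proportions (18 df), a stand-in for the planned model.

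| q | d (points) | Shift, MTM − PGx (points) | False-positive rate, ICC 0 | ICC 0.05 |
|---|---|---|---|---|
| 20% | +20 | −4 | 12.2% | 9.0% |
| 20% | 0 | 0 | 4.9% | 5.0% |
| 20% | −20 | +4 | 10.9% | 8.5% |
| 10% | +20 | −2 | 6.6% | 6.1% |
| 30% | +20 | −6 | 20.3% | 13.7% |

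Analysed as allocated, the bias is about zero and the rate is 4.8–5.2% in every row.

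**When MTM does help.** At q = 20% and d0 = 20, exclusion differs from the as-allocated result by 4 points if t = 0, by 2 if t = 10 and by 0 if t = 20.

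**Precision.** Going from 180 to 144 patients in one arm raises the standard error by √[(1/180 + 1/144)/(2/180)] = 1.061 at ICC 0, and by 1.032 at ICC 0.05. Lost patients are a minor matter; the selection is what counts.

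**The case against.** **The size is entirely assumed, and may be small.** The clause is a contingency, recent MTM is already barred, and PGx-only pharmacists need no MTM training. At q = 5% and d = 20 the bias is 1 point and the false-positive rate about 5.3%. This stands as a limit on size, but it does not remove the asymmetry.

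**The lead example works against the trial's hypothesis.** Of its roughly 12% rejections, about 11.6 points find MTM worse and 0.4 find it better. That is correct. Only a negative *d* inflates false claims of benefit. With a positive *d*, a real benefit is understated.

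**Adjustment might help.** The plan collects age, education, health literacy and co-medications, and mentions multivariate analyses. It names no covariates for this purpose, and adjustment cannot restore patients who were removed.

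**Analysis as allocated does not guarantee balance.** Random assignment is described only if more than 10 MTM-capable pharmacies are interested, and patients are recruited after allocation. With indicated shares of 30% and 10% at entry and a 20-point deficit, a 4-point bias remains as allocated. The planned fallback to ordinary logistic regression can also raise the error rate: ignoring clusters at ICC 0.05 gives about 15%, an upper bound for the planned procedure. Both are real but separate weaknesses. The near-5% figure describes removal of this one source, not the whole plan.

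**Exclusion keeps a pure testing-only arm.** This is the strongest point. Keeping patients who receive MTM dilutes a strict testing-only versus testing-with-MTM contrast by q × t: 2 points at q = 20% and t = 10, 4 points at t = 20. Exclusion does not deliver that contrast either, because the MTM arm still holds the counterparts of the removed patients. It distorts the contrast by q × d0, which is 4 points at d0 = 20. Retention distorts it more only if t exceeds d0. What stands is that the plan must say which question it answers.

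**Conclusion.** The concern holds and should be settled before enrolment. The one-sided exclusion after allocation is explicit in the text, nothing in the plan offsets it, and it reaches the primary outcome. What is established is that it can bias the comparison, not that it will by a known amount. The shift is −q × d, and neither quantity is in the documents. Over the ranges tabulated it runs from 6 points against MTM to 4 points in its favour, with false-positive rates from about 5% to 20%. It is zero if need for MTM is unrelated to outcome. These figures assume 70% comprehension, equal arms of 180, the same share of indicated patients in both arms at entry, no true MTM effect, and the stand-in test described above.

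**What to change.** Leave care as it is and replace only the exclusion clause under PGx Testing Only Arm, for example:

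> Patients in the PGx-only arm who receive MTM because it is clinically indicated remain in the study. They are invited to the follow-up survey where they consent, their refill data are collected, and the primary analysis counts them in the arm to which their pharmacy was allocated.

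Then:

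- In Data Analysis, state that the primary analysis compares the two delivery policies as allocated. Define its population as all tested patients with the outcome, by the pharmacy's allocated arm.
- In the patient log, record any MTM given in the PGx-only arm and whether it came before or after the result. Report the count per pharmacy.
- Present the analysis without these patients only as a sensitivity analysis, labelled as selected.

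The cost is one clause, a short statement of the question and population, one log field and one table row. Follow-up still depends on survey consent. The price in interpretation is the q × t dilution of the strict contrast, which is why the as-allocated question has to be written down.

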The provision of PGx testing is a logical extension of services provided at the community pharmacy for several reasons. **First**, pharmacists have experience with clinical testing and have expressed an interest in personalized medicine and PGx testing.⁴³⁻⁴⁵ In addition, pharmacists are interested in providing MTM services⁴⁶ as evidenced by the increasing number of MTM providers,⁴⁷ and development of new partnerships^{48,49} and business strategies.^{50,51} **Second**, patients are interested in PGx testing, particularly those that have experienced ADRs⁵² and appear to be receptive of new services offered by community pharmacists, including MTM.⁵³ For example, one study reported that more than half (52%) of the patients completed the home fecal

immunochemical test, demonstrating acceptance of a lab test offered by pharmacists.⁵⁴ Similarly, a pilot study of PGx testing offered as a stand-alone service in a single community pharmacy reported 43% uptake.⁵⁵ We surveyed community pharmacies offering PGx testing and found patient uptake to be relatively high (81%). **Third**, physicians' acceptance of pharmacist recommendations suggests that pharmacists can help prescribers apply PGx results to decisions regarding dosing or selection, reducing the burden on physicians^{55,56}. **Therefore, pharmacists' expert knowledge of drugs, patient and pharmacist interest in PGx testing and MTM, and physician acceptance of pharmacists' recommendations combine to support an optimal delivery model of PGx testing in the community pharmacy setting.**

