- In-person MTM (required only of pharmacists randomized to MTM + PGx testing arm): The purpose of this CE is to review elements of MTM, development of medication action plans, and incorporation of PGx testing into an MTM session. The development of this module was adapted from the MTM module offered by the American Pharmacists' Association (APhA). Attendance may be waived if the pharmacist provides proof of completion of the APhA MTM CE program.

PART II. PHARMACOGENETIC TESTING IN COMMUNITY PHARMACY TRIAL

Part II of the study will involve the cluster randomized trial to compare the effect of PGx testing as a stand-alone service to PGx testing with MTM (Figure 1/Aim 2)). We aim to enroll 20 pharmacist (in 20 separate pharmacies) and 360 patients in the study (~18 per pharmacy).

PGx Testing. Testing will be available for patients with active prescriptions for the drugs listed in Table 1. The drugs were selected based on CPIC guidelines and/or drug labels with PGx information that are likely to be filled at community pharmacies. If new CPIC guidelines are developed by the start of the study, we will update the list accordingly. Testing for each of the genes listed in the table will be provided by the CLIA-certified laboratory Pathway Genomics (CLIA # 05D1092505; San Diego, CA). The test for this study is a customized panel test that includes CYP2D6, CYP2C19, CYP2C9, SLC01B1 and VKORC1/CYP2C9. Currently, turnaround time for testing is 7-10 days. Given the varying coverage policies for PGx testing, all test fees will be supported by the study.

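### The control criteria let patients who were invited to testing and declined serve as matched controls, which can bias the untested comparison of refill adherence and medication changes

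*Combined protocol and SAP*

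**What the plan says.** The control rules are in the protocol's Part II, under Patient Study Population. On source: "Patients in the control arms will be identified by each participating pharmacy". On number and matching: "two controls will be identified per each participant in the PGx arms (2:1) and matched on drug, age and gender". On exclusion, judged from pharmacy records: "patients who have undergone MTM or PGx testing outside of the study will be excluded from the control arm". No other control exclusion is stated. The Overview of the Investigational Plan adds only that the control group is a 2:1 matched pharmacy population. The Patient Surveys section lists data items for controls but no selection rule.

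The same Part II section describes recruitment. Each pharmacy queries its database for active prescriptions of the eligible drugs and contacts the patients found. "If more than 30 patients in a pharmacy are identified by the database search", the newest prescriptions are to be contacted first. The PGx Testing paragraph adds that, once a patient shows interest, the prescriber must return a signed form before the patient is invited in to discuss testing.

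Time on treatment, medication changes and refill history are collected for controls and compared with the testing arms. The Survey Data Analysis section gives no method for that comparison.

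**The concern.** Both randomised arms receive testing, so the control group is the only concurrent untested comparator for refill adherence and medication changes. The protocol hypothesises that testing improves adherence, and pharmacy refill data run for 6 months after results are given.

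Tested patients have, by definition, accepted a pharmacist's offer. It is plausible, though the documents do not measure it, that people who accept are more engaged with their medicines than people who refuse. If those who refused can enter the control group, part of any adherence difference reflects who said yes rather than what testing did, and it points the way the protocol expects. Matching on drug, age and gender does not address this, and no adjustment is planned.

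**Working it through.** **Inputs.** 20 pharmacies and 18 patients each (Part II: "we estimate that we would need to enroll 18 patients per cluster (360 total"); 2 controls per participant (same section); uptake of 43% (Significance: "a pilot study of PGx testing offered as a stand-alone service in a single community pharmacy reported 43% uptake") and 81% (same paragraph, the team's own survey of pharmacies offering testing).

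**The plan's own figure.** 20 × 18 = 360, as stated.

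**Control places.** 2 × 18 = 36 per pharmacy; 2 × 360 = 720 overall. The plan implies these totals but does not state them.

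**Approached but not enrolled.** With uptake u, enrolling 18 means approaching 18/u and leaves 18/u − 18. Their largest possible share of the control places is s = (18/u − 18)/36.

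| Uptake u | Approached 18/u | Not enrolled | Share s of 36 places |
|---|---|---|---|
| 43% | 41.9 | 23.9 | 66% |
| 50% | 36.0 | 18.0 | 50% |
| 60% | 30.0 | 12.0 | 33% |
| 81% | 22.2 | 4.2 | 12% |

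These are upper bounds on decliners: some of those not enrolled will lack the prescriber's signature, and matching will remove others.

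**Effect on the comparison.** Let d be the adherence gap between acceptors and decliners in the absence of testing. This is an assumption. Suppose also that everyone not enrolled is a decliner, that unapproached patients are the same mix as approached ones, and that the 2:1 ratio is filled. Then, relative to acceptors:

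- decliners are lower by d;
- unapproached patients are lower by (1 − u)d;
- controls with decliner share s are lower by s·d + (1 − s)(1 − u)d.

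Allowing decliners therefore adds s·u·d to the spurious difference. Since s = (1 − u)/(2u), this equals d(1 − u)/2:

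- u = 43%: 0.57d/2 = 0.285d, on top of the 0.57d that remains with unapproached controls;
- u = 81%: 0.19d/2 = 0.095d, on top of 0.19d.

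If d were 10 points of proportion of days covered (illustrative only), the addition would be 2.85 or 0.95 points with no effect of testing; if d were zero it would be zero. Excluding decliners takes away one third of the total self-selection difference in this model, since (1 − u)/2 ÷ [3(1 − u)/2] = 1/3. The rest remains because volunteers are still compared with people who were never asked.

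**The case against.** The strongest reply is that the text is silent rather than wrong, and that several stronger conclusions a reader might draw go beyond it. Four parts of that reply stand.

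- **Timing.** A reader might infer that controls are picked after patients have been approached. Matching to each participant suggests it, but the protocol states no timing.
- **The 2:1 ratio.** A reader might infer that it cannot be reached, because 30 − 18 = 12 is far below 36, and the approached pool supplies two per participant only if 18/u − 18 ≥ 36, that is, uptake of one third or lower. But controls are not limited to approached patients, and 30 is a rule about whom to contact first, not a stated cap. The shortfall is not a defect of the plan as written.
- **Mostly refusers.** A reader might infer that the control group would consist largely of refusers. With 2:1 filled, decliners can reach half of it only at uptake of 50% or lower; at 81% they are at most about one eighth. Nor are they closer matches: an unapproached patient of the same drug, age and gender matches equally well.
- **Reach.** Comprehension, the primary outcome, is compared between the two testing arms and does not involve controls.

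The reply does not dispose of the gap itself. Nothing in the control criteria, the Overview, the survey section or the analysis section keeps decliners out or allows for them. Figure 1 is not available in the text reviewed and may carry further detail on the control arm.

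**Conclusion.** The point holds as a gap in the control criteria that should be closed. Patients who were offered testing and did not take it up are eligible controls, and could fill at most about 66% (uptake 43%) or 12% (uptake 81%) of the places at each pharmacy. The direction of bias, towards a benefit of testing on adherence, rests on the assumption that decliners are less adherent than acceptors. Its size depends on a gap that the documents do not give. The consequence is confined to the secondary, non-randomised comparison of refill adherence and medication changes. The documents do not support saying that the control group will be mainly refusers or that the matching ratio is unattainable.

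**What to change.** In the control paragraph of Patient Study Population:

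1. Make patients who were invited to testing and declined, or did not respond, ineligible for the main control group. Draw controls from patients not approached, and state when approach status is judged.
2. Record approach status for every control. For those approached, add the reason for not enrolling, so that refusal can be told apart from a missing prescriber signature.
3. Match on or adjust for baseline time on treatment, which is already collected. This is needed because, if "more than 30 patients in a pharmacy are identified by the database search, we will ask pharmacists to contact patients with the newest prescriptions", so the unapproached patients left as controls would tend to have older prescriptions.
4. Where a pharmacy has too few unapproached patients, accept fewer than two controls per participant, or none. Do not fill the places with decliners.
5. Report decliners as a separate group in a sensitivity analysis.

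The cost is one exclusion line, a short form field, one covariate or matching factor and one extra analysis. The Data Safety and Monitoring Plan already has pharmacies report numbers approached and consented after the first month, so the tracking is partly in place. The downside is fewer controls, most of all in pharmacies where everyone eligible was approached, and slightly lower precision for this secondary comparison. Because self-selection is reduced and not removed, the comparison should still be reported as non-randomised.
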